- *Unmanaged depression:* We defined this as responding “no” or “I have never been depressed” to the question “Depression prevention means using effective methods to keep depression from occurring, or if it does occur, to keep it as mild and brief as possible. Effective methods include controlling negative thinking every day, engaging in healthy, pleasant activities on most days, exercising for 30 minutes or more on most days, practicing stress management on most days, and getting professional help when needed. Do you effectively practice depression prevention in your daily life?”
- *Stress at work:* We defined this as answering the question “During the last 30 days, how often have you found yourself stressed or worried about problems as work?” with “sometimes,” “fairly often,” or “very often.” (rather than “almost never” or “never”).

Table 6 provides summary statistics for employees who completed the PHA in the control worksites.

B3. Program participation data

At the individual employee level, we examine three different definitions of participation based on the number of modules completed. Each module had its own set of requirements that defined completion and incentives attached to participation or completion. Details of the modules and their requirements are provided in Appendix 1.

- **Modules completed:** We defined a continuous variable denoting the number of modules completed, which ranges from 0 to 12 over the course of the study period. This serves as the primary definition of participation for this analysis.

⁷ Ware JE, Kosinski M, Dewey JE, Gandek B. How to Score and Interpret Single-Item Health Status Measures: A Manual for Users of the SF-8 Health Survey. Lincoln RI: QualityMetric Incorporated, 2001.

- **Participation indicator:** We defined a binary indicator of participation based on completing at least one module. This is a secondary definition for this analysis.⁸
- **High participation:** We defined another secondary binary indicator based on completing 3 or more modules. We chose 3 modules as the threshold for high participation based on the distribution of the number of modules completed.

Table 7 shows summary statistics on participation overall and by module across the treatment worksites for phase 1 and for phase 2 of the wellness program.

V. Study Sample

A. Main sample and subsamples

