estimates of the effect of the treatment. Therefore, we model the impact of participation on outcomes using a two-stage least squares (2SLS) specification:

$$Y_{ijt} = \gamma_0 + \gamma_1 PARTICIPATION_{ijt} + \gamma_2 X_{ijt} + \mu_{ijt} \quad (3)$$

Where the endogenous *PARTICIPATION* variable is estimated via the first stage regression:

$$PARTICIPATION_{ijt} = \pi_0 + \pi_1 TREATMENT_{jt} + \pi_2 TIME_WORKED_{ijt} + \pi_3 TREATMENT_{jt} * TIME_WORKED_{ijt} + \pi_4 X_{ijt} + v_{ijt} \quad (4)$$

We include the exposure interaction in the first stage, parallel to our ITT estimates. The coefficient γ_1 in equation (3) identifies the effect of participation on outcomes.

On the left-hand side of the first stage, this base specification uses the continuous definition of participation, with values from 0-12, which indicates the number of modules an individual participated in during the 36-month study period. **Table 10** shows the results of first stage estimates for this and for our alternative definitions of participation (including indicators for completion of 3 or more modules of the program or completion of at least 1 module of the program). In robustness specifications, we use these alternative definitions of participation.

If no one in the control group receives the treatment, we can interpret the 2SLS estimates of the LATE as a treatment on the treated (TOT). Empirically, we expected this to be essentially true by construction because the control worksites did not receive the wellness modules. However, because we assigned employees to worksites based on their initial locations of employment at the beginning of the study period, a small number of employees who moved from control worksites to treatment worksites during the intervention period did receive an opportunity to participate in the program. This explains the fact that the control group means in **Table 10** are nearly, but not exactly, zero.

C. Addressing endogeneity concerns

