Additionally, our phase 1 analysis of the first 18 months used a different baseline specification that did not allow for treatment effects to vary with individuals' exposure (rather, weighting individuals by exposure). It also included a different sample, as 5 additional worksites from the previous secondary control group were added to the treatment group and another 5 to the primary control group at the 18-month mark. Therefore, to facilitate comparisons of results between this phase 2 analysis to those from phase 1, we will present results using the phase 1 statistical model and set of weights on the phase 2 sample, as well as results using the phase 2 model and weights on the phase 1 sample.

Specifically, we conduct the ITT and LATE analyses using the phase 1 specifications that include just a treatment dummy. The ITT specification is:

$$Y_{ijt} = \beta_0 + \beta_1 TREATMENT_{jt} + \beta_2 X_{ijt} + \varepsilon_{ijt} \quad (7)$$

¹⁰ See, for example, Buntin and Zaslavsky, 2004; Manning, Basu, and Mullahy, 2005; Ellis and McGuire 2006; Jiang, Ellis, and Kuo, 2008.

The LATE specification is:

[figure not shown]
$$Y_{ijt} = \gamma_0 + \gamma_1 PARTICIPATION_{ijt} + \gamma_2 \mathbf{X}_{ijt} + \mu_{ijt} \quad (8)$$

With first stage regression:

$$PARTICIPATION_{ijt} = \pi_0 + \pi_1 TREATMENT_{jt} + \pi_2 \mathbf{X}_{ijt} + v_{ijt} \quad (9)$$

[figure not shown]
We conduct this analysis first for our full sample, and then for the subsample of treatment and control sites that match the phase 1 sample.

Figure 1: Locations of Treatment and Primary Control Worksites, Phase 2

Notes: This map shows the 25 treatment and 25 control worksites in Phase 2 of the treatment. Red markers designate treatment worksites; red triangles are the 5 additional treatment worksites that were added in Phase 2. Blue markers designate primary control worksites; blue triangles are the 5 additional primary control worksites that were added in Phase 2.

Figure 2. CONSORT Flow Diagram

Average number of employees per club = 304 (SD =88)
 Employees insured through Cigna during June 2016 (the midpoint of the study period) = 6,686 (37.34%)
 *Surveyed employees as a percent of all employees who worked between 8/1/2017 and 10/30/2017

Notes: This CONSORT diagram shows the flow of the trial and sample sizes through phase 2.

Table 1: Timeline of the Workplace Wellness Program

	Phase 1												Phase 2																							

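### The treatment-on-the-treated reading of the 2SLS estimates does not hold for the base model, whose coefficient is a weighted average effect per completed module

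*Combined protocol and SAP*

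**What the plan says.** Section VI.B asks what participating in the programme does to outcomes and answers with two-stage least squares. Equation (3), the second stage, contains PARTICIPATION and the covariates X. Equation (4), the first stage, contains TREATMENT, TIME_WORKED, their product and X: "We include the exposure interaction in the first stage, parallel to our ITT estimates".

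On the participation measure, "this base specification uses the continuous definition of participation, with values from 0-12". The values are counts of modules over the three years. Section IV.B3 says of the module count: "This serves as the primary definition of participation for this analysis". For the indicators of at least one module and of three or more modules, section VI.B says: "In robustness specifications, we use these alternative definitions of participation".

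The section then gives a single condition, no treatment received in the control group, under which "we can interpret the 2SLS estimates of the LATE as a treatment on the treated (TOT". It adds that a few control employees moved to treatment sites, so the condition is nearly but not exactly met.

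Section VI.F plans a simpler version for comparison with phase 1: "we conduct the ITT and LATE analyses using the phase 1 specifications that include just a treatment dummy" (equations (7) to (9)).

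**The concern.** Absence of control uptake turns an instrumental-variable estimate into a treatment-on-the-treated (TOT) effect when treatment is binary and assignment is the only excluded instrument. The base model departs from this in two ways that the TOT sentence does not mention.

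- **Unit.** With a module count, the coefficient γ1 is an effect per completed module. The effect on those treated is an effect per participant.
- **Instruments.** With TREATMENT×TIME_WORKED as a further instrument, γ1 weights employees differently from a TOT whenever uptake varies with hours.

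A third problem lies in the printed equations. TIME_WORKED is in equation (4) but not in equation (3), and it is not among the covariates listed for X in section VI.A or in the notes to Tables 3-6. Equation (1) writes it separately from X. Taken literally, a non-randomized variable is then an excluded instrument.

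The stake is how column 3 of Tables 3-6 will be read. It is headed only as linear 2SLS, with no unit. Its notes cite an equation (2), a number that no equation in the text carries. Phase 1 used the any-module indicator as its primary definition (footnote 8). A base estimate several times smaller than a phase 1 estimate could be taken for a weaker programme when only the unit has changed.

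**Working it through.** **1. Reproduce the plan's own figure.** Table 7, Panel B gives 7,288 treatment-site employees, 2,071 participants, and 1.17 modules per employee. Modules per participant = 1.17 × 7,288 / 2,071 = 4.12, against 4.11 stated (rounding). Participation = 2,071 / 7,288 = 28.4%, as stated.

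**2. The plan's stated condition.** The share of treated people who would take part whatever their assignment is the control mean / (control mean + first stage) for any module in Table 10. It runs from 0.21 / (0.21 + 27.53) = 0.8% to 3.07 / (3.07 + 62.25) = 4.7%. Control uptake is therefore a minor issue.

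**3. Scale.** With TREATMENT as the only instrument:

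- per participant = ITT / first stage (any module)
- per module = ITT / first stage (modules)
- ratio = first stage (modules) / first stage (any module)

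I read the Table 10 coefficients as average effects of assignment. This fits Table 7: 1.12 + 0.01 = 1.13 modules, against 1.17 unadjusted.

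| Table 10 sample | Modules | Any module | Ratio |
|---|---|---|---|
| All employees | 1.12 | 0.2753 | 4.07 |
| PHA | 3.45 | 0.6306 | 5.47 |
| Cigna | 3.13 | 0.5731 | 5.46 |
| Stably employed, all | 2.56 | 0.4975 | 5.15 |
| Stably employed, surveyed | 5.41 | 0.7922 | 6.83 |
| Stably employed, Cigna | 3.41 | 0.5954 | 5.73 |
| Worksite, all | 1.17 | 0.2819 | 4.15 |
| Worksite, surveyed | 3.49 | 0.6225 | 5.61 |
| Worksite, Cigna | 3.18 | 0.5729 | 5.55 |

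The three-or-more indicator does not give a TOT either. Of participants, 100 − 58.8 = 41.2% completed one or two modules and would be coded as untreated.

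**4. What the interaction does to the factor.** The ratios above are exact only for a single instrument. A simulation of two million records shows the departure in the full sample. Assumptions: exposure is Beta-distributed with mean 416.69 / 1,096 = 0.38 and SD 399.87 / 1,096 = 0.365 (days worked standing in for TIME_WORKED); the first stage is scaled to 27.53% and 4.07 modules per participant; TIME_WORKED is included in the second stage. TOT divided by γ1 was:

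- constant per-module effect: about 4.0-4.2
- effect rising with exposure, uptake rising with exposure: about 3.6-3.8
- effect falling with exposure, uptake rising with exposure: about 5.9-6.4

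**5. Weighting.** With one instrument, hours groups count in proportion to their first stage. With the interaction added, they count roughly by its square. Under the same assumptions, if uptake rises in proportion to exposure, mean exposure is about 0.73 among participants, 0.73-0.80 for the single-instrument per-module estimate, and 0.83-0.89 with the interaction. If uptake does not vary with exposure, it is 0.38 throughout.

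**6. TIME_WORKED omitted from equation (3).** Give time worked a direct effect of 0.5 on the outcome across the full exposure range (residual SD 1, assumed), with uptake rising with exposure and a true per-module effect of −0.10. Equations (3) and (4) as printed then return about −0.01. Where the per-module effect falls with exposure, the sign reverses. If uptake does not vary with exposure, the bias disappears.

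**The case against.** The strongest reply is that the ratio is a change of unit and not a bias, and that the unit is disclosed. The plan states the 0-12 range, explains in footnote 8 why it left the any-module indicator, and prints both first stages, so a reader can convert. With one instrument the numerator is the same and the test is essentially unchanged. The binary definitions and the treatment-dummy model are already planned, the latter expressly to ease comparison with phase 1. The TOT sentence is conditional and mainly introduces the employees who changed site.

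Much of this stands. Nothing here shows a wrong ITT result or a hidden unit, and the count is a defensible choice. But the TOT sentence follows the base specification directly and is not limited to the binary versions. The results tables carry no unit. Equations (8)-(9) do not say which participation measure they take, and the planned comparison also carries the phase 1 weights, which weighted individuals by exposure.

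A reader might go further and infer that the base estimate mostly describes long-hours staff. The documents do not support that. The interaction coefficient π3 is not reported. That it is positive is plausible (2.56 modules in the stably employed against 1.12 overall), but it is an inference. Even then, γ1 changes only if the per-module effect varies with hours. Stable employment at baseline is also a poor stand-in for hours: days worked among stably employed controls average 786.57 with an SD of 376.96. Nor would such a reading set the two estimands clearly apart, since roughly 2,344 × 50.3% / 2,071 = 57% of participants are already stably employed.

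**Conclusion.** The TOT statement is wrong as written for the base model. No control uptake suffices only with a binary participation measure and TREATMENT as the sole excluded instrument. In the base model γ1 is a weighted average effect per completed module.

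The scale gap is 4.1 to 6.8 across the nine Table 10 samples for single-instrument estimates, taking the table's coefficients as average effects of assignment. It should not be quoted as an exact factor for the base estimator. A shift of weight towards high-hours staff is possible but conditional on π3 > 0, and it matters only if the effect per module differs by hours.

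The missing TIME_WORKED term may be only a slip of notation. If it is literal, γ1 is biased wherever hours affect outcomes directly and uptake varies with hours, and the scale factor would not survive. The size of that bias cannot be worked out from the documents; the simulated values show only that it could be large.

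**What to change.** 1. Label γ1 in column 3 of Tables 3-6 as the average effect per completed module, and correct the notes' reference to equation (2).
2. Limit the TOT wording to the at-least-one-module model with TREATMENT as the only excluded instrument. State that PARTICIPATION in equations (8)-(9) is the any-module indicator, state which weights that model uses, and show it beside the base estimate.
3. Put TIME_WORKED in equation (3) for the base model, as in equation (1). Because section VI.C counts time worked among the primary outcomes, this does not make it a baseline covariate, which is a further reason to show the treatment-only estimate.
4. Report π1 and π3 for each sample, so that readers can judge whether the interaction moves the weights.

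The cost is one extra column and slightly longer table notes. Precision is not an obstacle: the any-module first stage has t of at least 17 in every Table 10 sample, the smallest being 49.75 / 2.82 = 17.6 in the stably employed.

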Four modules were offered during the next 18 months (phase 2): “Healthy and Fit,” which combined healthy eating patterns and regular exercise to avoid weight gain during the holiday season; “Step Challenge,” which was a team-based module, focusing on increasing physical activity by using a fitness device to track steps; and two consecutive “Nutrition for a Lifetime” modules, which were designed to help employees achieve and maintain a healthy lifestyle by combining healthy nutrition, exercise, stress management and sleep patterns. In addition, participants had the opportunity to log their step counts using a wearable device and this information was gathered between January 2017 and July 2017. Please refer to Appendix 1 for detailed information on the components of the wellness program by module, including requirements and incentives. Employees had opportunities to receive incentive payments through completion of the PHA and the biometric screenings, in addition to participation in the individual modules of the program.

In each treatment worksite, a Registered Dietitian employed by Wellness Workdays coordinated and led the wellness programming. The Registered Dietitians engaged employees in the wellness program modules, educated them about the content of the program, and led employees in various creative activities such as group fitness and cooking demonstrations. Each Registered Dietitian had the flexibility to tailor the day-to-day programming around the themes of the modules. The Registered Dietitians spent approximately 8 hours per week at each worksite.

III. Randomization

The wellness program was implemented in a randomly selected subset of BJ’s Wholesale Clubs. Each club is a standalone worksite, with an average of 118 employees at any given time. At the beginning of the study, there were 201 BJ’s worksites in the U.S. along the East coast, extending from Maine to Florida. We eliminated 41 worksites because they were geographically remote or had employee pools with substantially different insurance coverage from the others, leaving 160 worksites in our sample.

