Among these worksites, we randomly selected 25 “treatment” worksites that would receive the wellness program and 25 “primary control” worksites for phase 2.⁵ These primary control worksites participated in data collection through PHAs and in-person biometric screenings, but did not receive the wellness program treatment. **Figure 1** shows the locations of the 25 treatment and 25 control worksites across the Eastern U.S. The remaining 110 worksites served as “secondary controls.” which were included in analyses of administrative data. Thus, the primary data described below was collected from the 50 treatment and primary control worksites; administrative data were compiled for all 160 worksites. **Figure 2** shows a Consolidated Standards of Reporting Trials (CONSORT) flow diagram for our phase 2 evaluation, including the sample sizes of treatment and control groups.

⁵ For the first 18 months of the study (phase 1), there were 20 treatment and 20 primary control sites.

Randomization at the worksite level allows us to assess the effects of interventions that aim to affect workplace culture or operate on a group level, such as using common break rooms to stage nutrition demonstrations, team-based activities, or worksite level prizes.

IV. Data

Our analysis focuses on outcomes from five data categories. The Table below displays the source of each data set and the study population from which it is derived.

Summary of the Components of Data Collected				
Data	Source	Treatment Worksites (25)	Primary Control Worksites (25)	Secondary Control Worksites (110)
Administrative Data				
Employment records	BJ's	All employees	All employees	All employees
Claims data (medical and pharmaceutical)	Cigna (via BJ's)	Employees insured by Cigna	Employees insured by Cigna	Employees insured by Cigna
Primary Data				
Biometric screening data	Wellness Workdays	Employees completing screening	Employees completing screening	None (by design)
Personal Health Assessment	Wellness Workdays	Employees completing survey	Employees completing survey	None (by design)
Participation in the treatment	Wellness Workdays	All employees	None (by design)	None (by design)

A. Administrative Data

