The key identifying assumption is that the only mechanism through which being employed in a treatment worksite affects outcomes is through the availability of the wellness program. There are two threats to this assumption. First, to the extent that covariates were not balanced at baseline and those covariates affect the outcomes of interest, that imbalance could bias our estimates. We control for observed covariates and apply weights to balance covariates between treatment and control. Despite these adjustments, unobserved covariates might still be imbalanced.

Second, to the extent that the wellness program affected hiring or tenure of employees, their presence in the data set may be endogenously determined. We address the issue of endogenous entry by pre-specifying a subsample of those who were already employed at the time the intervention began. We defined this more restrictive “stable employment” subsample as comprising employees who had worked continuously for 13 weeks prior to the wellness program. This comes at a cost of reducing the overall sample size. Our goal in choosing the definition for this subsample was to balance the costs and benefits, as detailed in Appendix 2.

In this stably employed subsample, however, exit from the firm's workforce is still potentially endogenous. We deal with this concern in two ways. First, we will test balance on exit between treatment worksites vs. from control worksites overall and for subgroups. Indeed, tenure and time worked are among our primary outcomes. To the extent that we observe any unbalanced exit, we will perform a bounding exercise (assuming that those who exited have outcomes working against any observed effects of the intervention).

D. Subgroup analyses

We pre-specified three subgroup analyses. We selected these subgroups based on differences in key outcomes within the control group for those with different baseline characteristics, such as differences in medical spending by age or in reported exercise by sex (**Table 11**).

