Notes: The average participation rate for each module was calculated as the percentage of individuals who completed a module out of all who were eligible to complete a module during the time that the module was running. Participation is equivalent to completion of a module, with an incentive of a gift card for completion of the module. Descriptions of each module and their criteria for completion are provided in Appendix 1. Employees could only participate in the Take Charge of Your Health module once, though it was run twice. Club Cardio Challenge had two rounds and completion of either round 1 or round 2 earned a gift card; completion of both rounds did not earn an additional gift card, but rather an entry into a raffle for a Fitbit, unless the employee had Cigna health insurance, in which case they could complete both rounds of Club Cardio Challenge for an additional fitness reimbursement. Nutrition for a Lifetime occurred in two rounds; individuals who completed round 1 earned an ActivBAND or gift card. Completion of round 1 and round 2 earned an additional gift card or weight management reimbursement for Cigna members. Values were weighted by the number of days an individual was working during a given module's timeframe.

Panel B. Intensity of Participation by Definition

Definition of Participation	Employees at Treatment Worksites (N = 7288)	Participants at Treatment Worksites (N = 2071)
Completed any module (%)	28.4	100.0
Modules completed (#)	1.17	4.11
3 or more modules (%)	16.7	58.8

Notes: These summary statistics show the intensity of participation in the treatment group according to the 3 definitions of participation. In contrast to Panel A above, the sample (denominator) for these calculations was all employees at treatment worksites (first column) and all employees at treatment worksites who completed any module (second column) throughout the study period. Because of this difference in the denominators, participation rates for a given module in Panel A could exceed the average participation study-wide in Panel B.

Table 8: Balance Between Treatment and Control—Employee Level**Panel A.1: All Employees – Unweighted**

	(1)	(2)	(3)	(4)	(5)
	Treatment (n=7288)	Primary Control (n=7377)	Primary + Secondary Control (n=41376)	(1) vs (2) P value	(1) vs (3) P value
Demographics					
Age (yrs)	33.5	32.8	33.0	0.333	0.358
Female (%)	46.9	46.8	45.6	0.942	0.444
Race (%)				<0.001	<0.001
Black	21.1	25.2	26.7		
White	57.7	51.6	48.8		

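### The 2SLS estimate is an effect of participation only if employees who complete no module are unaffected, an assumption the plan neither states nor tests

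*Combined protocol and SAP*

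**What the plan says.** Section IV.B3 gives the primary participation measure: "We defined a continuous variable denoting the number of modules completed, which ranges from 0 to 12 over the course of the study period". The notes to Table 7 add that "Participation is equivalent to completion of a module". An employee who completes no module is therefore coded zero, whatever else he or she was exposed to.

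Section VI.B uses assignment, and assignment interacted with time worked, as instruments for this count. It says that the coefficient γ1 "in equation (3) identifies the effect of participation on outcomes". It then allows a treatment-on-the-treated (TOT) reading on one condition, that controls do not receive the program.

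Section VI.C gives the identifying assumption: "the only mechanism through which being employed in a treatment worksite affects outcomes is through the availability of the wellness program". It continues, "There are two threats to this assumption", and names baseline imbalance and endogenous entry or exit.

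On how the program works, section III justifies randomizing worksites because this allows study of "interventions that aim to affect workplace culture or operate on a group level", with break-room demonstrations, team activities and worksite prizes as examples. Section II says that a dietitian, on site about 8 hours a week, "led employees in various creative activities such as group fitness and cooking demonstrations".

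**The concern.** The stated assumption and the claimed estimand do not match. If assignment acts only through the program being available, the ITT is the effect of the program. To divide that effect by modules completed and call the result an effect of participation, assignment must act only through completed modules. The plan does not state this stronger exclusion restriction, and its reason for randomizing worksites gives grounds to doubt it.

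If a break-room demonstration or a change in workplace culture affects someone who completes nothing, that effect enters the numerator of the LATE while the person adds nothing to the denominator, so the effect is credited to completers. The TOT condition does not help, because it deals with crossover by controls and not with effects on non-completers at treatment sites.

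At stake is the reading of column 3 in Tables 3–6, and of the worksite-level LATEs in section VI.E, which use the same instrument. The sensitivity analyses in section VI.F change the participation definition, but every definition keeps the restriction.

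**Working it through.** **Reproducing the plan's participation figures (Table 7, Panel B).** 2,071/7,288 = 28.42% (stated 28.4%). 4.11 × 0.2842 = 1.168 modules (stated 1.17). 58.8% × 0.2842 = 16.71% (stated 16.7%). Raw treatment-minus-control differences are 28.4 − 0.21 = 28.19 points and 1.17 − 0.01 = 1.16 modules. The Table 10 first stages are 27.53 and 1.12. They are weighted and covariate-adjusted, so a small gap is expected and is not an error.

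**Base definition (modules completed).** Let g be the true effect per module, F the first stage, and suppose assignment also shifts every treatment-site employee by d × g. Then ITT = gF + dg. Treating γ1 approximately as ITT/F,

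LATE/g = 1 + d/F.

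F is from Table 10, Panels A and B. The values of d are assumptions.

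| Sample | F | d = −0.25 | d = 0.25 | d = 1.0 |
|---|---|---|---|---|
| All employees | 1.12 | 0.78 | 1.22 | 1.89 |
| Stably employed | 2.56 | 0.90 | 1.10 | 1.39 |
| Cigna | 3.13 | 0.92 | 1.08 | 1.32 |
| PHA | 3.45 | 0.93 | 1.07 | 1.29 |

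**Any-module definition (robustness).** Let p be the first stage, τ the effect on completers, and kτ the effect on non-completers. Then ITT = pτ + (1 − p)kτ, so

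LATE/τ = 1 + k(1 − p)/p.

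The values of k are again assumptions.

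| Sample | p | (1 − p)/p | k = −0.1 | k = 0.1 | k = 0.25 |
|---|---|---|---|---|---|
| All employees | 0.2753 | 2.63 | 0.74 | 1.26 | 1.66 |
| Stably employed | 0.4975 | 1.01 | 0.90 | 1.10 | 1.25 |
| Cigna | 0.5731 | 0.745 | 0.93 | 1.07 | 1.19 |
| PHA | 0.6306 | 0.586 | 0.94 | 1.06 | 1.15 |

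With k = 0 the ratio is 1 in every row. A simulation of this simple ratio at p = 0.2753 gave 0.74, 1.00, 1.27 and 1.65 at k = −0.1, 0, 0.1 and 0.25, in line with the formula.

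**Three-or-more definition (robustness).** Here employees with one or two modules are also coded zero. Even with no effect on those who complete nothing, if one or two modules give half the effect of three or more, the ratio in all employees is [15.95 + 0.5 × (27.53 − 15.95)]/15.95 = 1.36.

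**The case against.** The best reply is that the plan puts the ITT first, calls the LATE a distinct question, and heads column 3 simply 2SLS (Linear). It nowhere makes the LATE the basis for its conclusions. The sentence in section VI.C is not itself wrong, since an availability assumption is compatible with culture effects. All of this stands and limits the point to what is claimed for γ1.

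Two stronger readings are tempting, and the documents support neither.

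- A reader might infer that the participation effect *is* overstated. The documents give neither the size nor the direction of any effect on non-completers.
- A reader might infer that the program reaches everyone. Section III speaks only of aims, and several of the activities are tied to modules: dietitians built programming around module themes, the worksite trophies belong to the Club Cardio Challenge, and the team contest is Module 12. Non-completers could be exposed to such activities, but the text does not say that they were.

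The largest ratios also need care. The all-employee sample includes anyone employed for any length of time (mean control tenure is about 417 days, Table 3), and five treatment sites joined only at month 18. Many non-completers there had little exposure, so the direct effect is plausibly smallest where the multiplier is largest.

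Finally, both formulas approximate the plan's weighted 2SLS, which also uses the time-worked interaction as an instrument.

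What remains is that VI.B asserts identification without the assumption it needs, VI.C counts two threats where this is a third, and no planned analysis relaxes the restriction.

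**Conclusion.** The point holds in conditional form. The 2SLS coefficient measures a participation effect only if assignment acts on outcomes solely through completed modules. The plan states a weaker assumption and describes group-level routes that could breach the stronger one.

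The LATE is overstated if non-completers are affected in the same direction as completers, unbiased if they are unaffected, and understated if the effect is opposite. The size rests on assumed values of d and k. For the base per-module estimate, d = 0.25 to 1.0 gives about 22% to 89% in all employees (the Table 3 sample) and 8% to 32% in the Cigna sample (Table 4). For the any-module version, k = 0.1 to 0.25 gives about 26% to 66% in all employees, 10% to 25% in the stably employed, 7% to 19% in Cigna and 6% to 15% in PHA. These figures show how sensitive the estimate is; they do not estimate the actual bias. The ITT and reduced-form worksite results do not depend on this restriction.

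**What to change.** 1. In VI.B–C, state the exclusion restriction in terms of modules completed, and list effects on employees who complete none as a third threat.
2. Replace the claim that γ1 "identifies the effect of participation on outcomes", and the TOT sentence, with a statement that the 2SLS result is *the ITT rescaled by participation, a participation effect only if non-completers are unaffected*. Put the same statement in the notes to column 3 of Tables 3–6.
3. Add one sensitivity analysis: rerun the planned 2SLS with Y − δ × TREATMENT as the outcome, over a prespecified grid of δ in outcome units that includes zero and negative values. Do this for the base per-module definition and for both alternatives. It keeps the plan's own instruments and weights, so it does not rely on the approximations above.

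The cost is wording, table notes and some extra regressions on data already held. The downside is a more cautious claim about participants.
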